4.1 General Study Design and Plan

A multicenter, prospective, interventional, randomized-controlled trial. Randomization will be in a 1:1 ratio, Test Arm (PCI + Cooling) or Control Arm (PCI alone). This is an unblinded trial with randomization using stratified by site using permuted blocks.

Subjects will be screened and randomized according to the following flow diagram:

[figure not shown]

Figure 1 Screening and Enrolment Flow

COPY

Follow-up after randomization (post-procedure, either Control with PCI only, or Test with PCI and Cooling) are described below:

[figure not shown]

Figure 2 All Patient Procedures

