4.2 Inclusion-Exclusion Criteria and General Study Population

4.2.1 Inclusion Criteria:

All Inclusion Criteria must be answered YES for subject to satisfy Inclusion Criteria:

1. The patient is ≥ 18 years of age.
2. The patient must have symptoms consistent with AMI (i.e. chest pain, arm pain, etc.) and unresponsive to nitroglycerin, with symptoms beginning greater than 30 minutes but less than 6 hours prior to presentation at hospital.
3. Qualifying Infarct location:

Roll-In subjects: Evidence of Acute Anterior or Inferior MI with ST- segment elevation of ≥ 0.2 mV in two or more anterior or inferior contiguous precordial leads (V1 –V4).

Randomized subjects: Evidence of Acute Anterior MI only with ST-segment elevation of ≥ 0.2 mV in two or more anterior contiguous precordial leads.

4. The patient is eligible for PCI.
5. The patient is willing to provide written informed consent to participate in this clinical trial.

4.2.2 Exclusion Criteria:

All Exclusion Criteria must be answered NO for subject to satisfy Exclusion Criteria:

1. The patient has had a previous Myocardial Infarction.
2. The patient is experiencing cardiogenic shock (systolic blood pressure [SBP] <100 mmHg, HR >100 bpm and arterial oxygen saturation (pulse oximetry) $\leq 95\%$ without additional oxygen
3. The patient is presenting with resuscitated cardiac arrest, atrial fibrillation, or Killip risk stratification class II through IV.

4. The patient has an aortic dissection or requires an immediate surgical or procedural intervention other than PCI.
5. The patient has known history of Congestive Heart Failure (CHF), hepatic failure, end-stage kidney disease or severe renal failure (clearance < 30ml/min/1.73m²).
6. The patient is febrile (temperature > 37.5 °C) or has experienced an infection with fever in the last 5 days.
7. The patient has a known previous CABG.
8. The patient has a known recent stroke within 90 days of admission.
9. Cardio-pulmonary decompensation that has occurred en route to the hospital or, in the opinion of the physician, that is imminent or likely to occur following presentation to the clinical site.

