4.4 Study Variables

Observations and records of important variables will be assessed according to the following schedule along with acceptable time-windows. Measurements outside scheduled assessment times will be considered protocol deviations.

Notable evaluations include the following:

COPY

For Control subjects:

Procedure/ Interval	Baseline / Enrollment	Immediately prior to reperfusion (PCI)Post-PCI	Catheter Removal	Discharge*	Follow-Up @ 4-6 Days	Follow-Up @ 30 Days (±7 days)	Follow-Up @ 12 months (±14 days)	Unscheduled Visit
Trial Eligibility & Informed Consent	upon arrival to hospital							
Physical Exam and Medical History	X			X				
Catheter Insertion Time	X							
Catheter Removal Time			X					
Temperature Documented	X							
Vital Signs	X							
Blood Studies RBC's, WBC's, Hct, Hgb, Platelets, Neutrophils, Eosinophils	X							
Pro BNP							X	
Lab Studies BUN, Creatinine, Na, K, Ca, Mg, Cl, P, lactic acid, glucose, amylase, lipase	X							
Any Medication Use	X	X	X	X	X	X	X	X
Troponin I or T	Collect at Baseline	Collected only if peak reached	Collected only if peak reached					
12 lead ECG	X							
Adverse Events		X	X	X	X	X	X	X
Cardiac Magnetic Resonance (cMR)					X			
NYHA Assessment							X	X
KCCQ Assessment							X	X

COPY

For Test subjects:

Procedure/ Interval	Baseline / Enrollment	Initiation of Cooling	Immediately prior to reperfusion (PCI)	Maintenance of Target Temp 32 ±1°C	Rewarming to 36°C	Catheter Removal	Discharge	Follow-Up @ 4-6 Days	Follow-Up @ 30 Days (±7 days)	Follow-Up @ 12 months (±14 days)	Unscheduled Visit
Trial Eligibility & Informed Consent	upon arrival to hospital										
Physical Exam and Medical History	X						X				
Anti-Shivering Protocol	X			X ^o							
Cold Saline Infusion		X									
Catheter Insertion Time		X									
Catheter Removal Time						X					
Temperature Documented	X	X	X	every 30 min during 3 hr cooling							
Temperature Data Download						X					
Vital Signs	X	X	X	every 30 min							
Blood Studies RBC's, WBC's, Hct, Hgb, Platelets, Neutrophils, Eosinophils	X			upon reaching target temperature	upon reaching normothermia						
Pro BNP										X	
Lab Studies BUN, Creatinine, Na, K, Ca, Mg, Cl, P, lactic acid, glucose, amylase, lipase	X										
Any Medication Use	X	X	X	X	X	X	X	X	X	X	
Troponin I or T	X	Collected only if peak reached	Collected only if peak reached	Collected only if peak reached	upon reaching normothermia, Collected only if peak reached	Collected only if Peak reached					

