6.3 Covariates and Subgroups

Subgroups to be evaluated for heterogeneity of infarct size using an interaction model with treatment variable and the following subgroup variable: age (<65 vs >65 years), BMI (<25 vs >=25), BMI (<30 vs >=30), sex, door to balloon time (<60 minutes, 60-90 minutes, >90 minutes), ischemic time (<4 hours vs >4 hours), post-TIMI flow (0-2 vs 3), temperature at PCI (<32°C, 32-35°C, >35°C). Wald test or t-test p-value will be reported for each group as appropriate depending on final linear regression model.

In order to evaluate clinical characteristics in association with infarct size, separate univariate models may be considered for exploratory analysis: ischemic time, country and/or center. Analysis of covariance models will be used. Evaluation for independence, normality, homoscedasticity, and linearity will be applied. Square root transformation will be used if assumption is violated. Beta coefficient, standard error, 95%CI, and p-values will be reported. From among the variables with individually significant associations, after selection of single covariates from among any collections of highly collinear covariates based on their univariate associations with infarct size, a multivariate model will be built using forward and backward stepwise variable selection, to determine the variables with independently significant associations with risk, using a criterion of $p \leq 0.05$.

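### SAP section 6.3 tests a treatment interaction with temperature at PCI, a result of cooling that only the Test Arm receives; the interaction is probably not estimable and should become a Test-Arm description.

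*SAP*

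**What the plan says.** Section 6.3 of the SAP plans a linear model of infarct size with treatment and its interaction with each of several subgroup variables. One of these is "temperature at PCI (<32°C, 32-35°C, >35°C". The section adds: "Wald test or t-test p-value will be reported for each group", subject to the form of the final model. Nothing confines the temperature item to the Test Arm.

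Section 4.1 randomises patients 1:1 to "Test Arm (PCI + Cooling) or Control Arm (PCI alone". In section 4.4 the Test schedule has a column headed "Maintenance of Target Temp 32 ±1°C". The row "Temperature Documented" is marked for Test patients at baseline, at the start of cooling, just before PCI, and then every 30 minutes while cooling lasts. The same row in the Control schedule carries one mark, at baseline. The only temperature limit at entry, in section 4.2, is an upper one: "The patient is febrile (temperature > 37.5 °C".

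Three outputs in section 13 bear on the point:
- The Cooling Procedure table includes wire-crossing temperature, is laid out by randomised arm and has a p-value among its statistics.
- The covariate association table includes temperature at PCI for ITT and PP, with no grouping and a p-value.
- The Temperature Over Time figure is grouped by randomised arm.

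The subgroup list in 6.3 also contains "age (<65 vs >65 years" and "ischemic time (<4 hours vs >4 hours".

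**The concern.** A subgroup interaction asks whether the treatment effect differs between kinds of patient. That needs a variable that treatment does not determine, and both arms represented in its categories. Temperature at PCI meets neither condition. Its bands largely record how far cooling had progressed by the time of PCI, and one arm is not cooled.

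Two things are at stake. First, a prespecified test may have no estimate. Second, software that meets aliased terms may drop them and still print a treatment coefficient. If Controls are all above 35°C, that coefficient compares a subset of the Test Arm, selected by its response to cooling, with the whole Control Arm. Reported under a subgroup label, it could be read as a treatment effect in patients above 35°C. The covariate association table has a related weakness: with the arms pooled, temperature at PCI is confounded with treatment.

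**Working it through.** **The plan's own figure.** The SAP gives no number for this interaction. Its sample size, used below only for scale, reproduces. With SD 12 %LV, difference 3.5 %LV, two-sided alpha 0.044 and 80% power (section 5):

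n per arm = 2 × (2.014 + 0.842)² × 12² / 3.5² ≈ 192, total 384, as stated.

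**The model.** Two arms and three bands give six cells. Taking >35°C as reference, the columns are an intercept, treatment, two temperature indicators and two treatment-by-temperature products: six coefficients. The model is saturated, so its rank equals the number of occupied cells, whatever the counts within them. Writing T and C for the arm means in a band:

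- treatment coefficient = T(>35) − C(>35)
- interaction at 32-35°C = [T(32-35) − T(>35)] − [C(32-35) − C(>35)]
- interaction at <32°C = [T(<32) − T(>35)] − [C(<32) − C(>35)]

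A coefficient is estimable only if every cell mean in it is observed. With Test patients in all three bands (an assumption; an empty Test band lowers the rank further):

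| Controls at PCI | Rank (of 6) | Treatment coefficient | Interaction terms estimable |
|---|---|---|---|
| no value | 3 | no | 0 of 2 |
| all >35°C | 4 | yes | 0 of 2 |
| some at 32-35°C, the rest >35°C | 5 | yes | 1 of 2 |
| some in all three bands | 6 | yes | 2 of 2 |

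A design-matrix check gave rank 3 with Controls missing. With all Controls above 35°C it gave rank 4 under each of four different assumed splits of the Test Arm.

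**The rank-4 row.** C(>35) is then the mean of the whole Control Arm, so the treatment coefficient is the mean of Test patients still above 35°C minus the mean of all Controls. Randomisation does not protect that comparison.

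**The rank-5 row.** With m Controls at 32-35°C, and a and b Test patients at 32-35°C and >35°C, the standard error of the one estimable term is 12 × √(1/m + 1/(192 − m) + 1/a + 1/b), hence more than 12/√m. The primary contrast has standard error 12 × √(2/192) = 1.22 %LV. For 12/√m alone to come down to that, m would have to be 192/2 = 96, half of an uncooled arm. The SAP gives no value for m, so no specific precision is claimed; if m is a few, the term is very imprecise. Section 6.4 records that enrolment was not completed, so real cells may be smaller. The ranks depend only on which cells are occupied.

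**Boundary values.** Age exactly 65 and ischemic time exactly 4 hours satisfy neither inequality. The BMI groups in the same list use >= and have no such gap.

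**The case against.** The strongest case on the other side concerns the Control data. The section 4.4 schedules are introduced as notable evaluations and need not be exhaustive. In the copy read here, two column headings of the Control table run together, so a mark could have been lost. The Cooling Procedure table, with wire-crossing temperature by arm and a p-value, suggests that Control values near PCI may have been expected, although that table also holds items that apply only to cooled patients. This stands. A reader might infer from the schedule that Controls were certainly not measured at PCI; the documents do not establish that, so the rank-3 case is secondary. It does not rescue the analysis: recorded Control values that all exceed 35°C still give rank 4.

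It can also be said that the position of Controls above 35°C is inferred. That stands too. A reader might conclude that the model cannot be run under any circumstances. The documents do not support so strong a claim, because Controls in a cooler band would make one or both terms estimable. Nothing in the SAP, however, would put substantial numbers of uncooled patients there.

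The harm is contingent as well. Section 6.3 leaves the p-value to the final model, and its reference to groups may mean one p-value per subgroup variable. Section 13 lists no display of treatment effects by subgroup. This limits the severity but leaves the specification faulty.

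Two further readings should be resisted. Test patients above 35°C at PCI are not thereby uncooled: cooling starts before PCI and continues after it, and section 13 lists patients not cooled separately. Nor does the point extend to door-to-balloon time, ischemic time or post-procedure TIMI flow. Both arms undergo PCI, and the SAP shows no comparable absence of one arm from their categories.

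**Conclusion.** The point holds at modest severity. As specified in 6.3, the interaction uses a variable produced by the treatment, and that fault remains however many cells are filled. Under the most plausible reading, with Controls all above 35°C, neither of the two interaction terms is estimable (rank 4 of 6), and the treatment coefficient left behind is not a randomised contrast. If Controls have no value at PCI, there is no treatment contrast at all (rank 3). A few Controls at 32-35°C would give one very imprecise term (rank 5).

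The aliasing follows from the model structure and is certain once the occupied cells are known. Which cells Controls occupy is an inference from their not being cooled. A reader might take this as a challenge to the trial's main result. It is not: the two-arm comparison in section 8.1 does not use temperature at PCI.

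**What to change.** 1. In section 6.3, delete temperature at PCI from the interaction list. State instead that infarct size by temperature at PCI, in the existing three bands, will be described in the Test Arm only (n, mean, SD), labelled non-randomised and with no treatment comparison.
2. In the covariate association table of section 13, limit the temperature-at-PCI entry to the Test Arm, label it exploratory and non-randomised, and match its statistics to item 1: descriptive, without a p-value.
3. Reconcile the Control schedule in section 4.4 with the Cooling Procedure table and the Temperature Over Time figure. State whether Control temperatures after baseline are recorded. If they are not, show Controls at baseline only and drop the between-arm p-value for wire-crossing temperature.
4. Minor: write >=65 years and >=4 hours, so that boundary values fall in a group.

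The cost is wording in 6.3 and 4.4 and changes to two table shells and possibly one figure shell. No new data or temperature cut-points are needed. What is given up is a formal treatment comparison by temperature at PCI, which a trial with one uncooled arm is unlikely to support.

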Association of infarct size with covariates	ITT and PP	Association with covariates including age, BMI, sex, pre-TIMI flow, post-TIMI flow, DTB, Ischemic time, and temperature at PCI	4-6 day	NA	p-value
NYHA classification at 12 months	ITT	NYHA Classification	12 months	Treatment	x (p%), p-value
KCCQ summary at 12 months	ITT	KCCQ overall summary score and KCCQ clinical summary score	12 months	Treatment	n, mean, SD, median, min, max, p-value

COPY

NT-proBNP summary at 12 months	ITT	NT-proBNP	12 months	Treatment	n, mean, SD, median, IQR, min, max, p-value
Clinical outcome summary (death, MI re-infarction, or TVR at 30 days)	Safety analysis set	MACE (Primary Safety)	30-days	Randomization	x (p%), p-value
Clinical components of mace summary	Safety analysis set	Additional Safety Endpoints	30 days	Randomization	x (p%), p-value
Subjects with serious adverse events summary within 30 days	Safety analysis set	All Serious Adverse Events	30 days	Randomization	x (p%), p-value
Subjects with non-serious adverse events summary within 30 days	Safety analysis set	All Non-Serious Adverse Events	30 days	Randomization	x (p%), p-value
Subjects with serious adverse events summary within 12 months	Safety analysis set	All Serious Adverse Events	12 months	Randomization	x (p%), p-value
Subjects with non-serious adverse events summary within 12 months	Safety analysis set	All Non-Serious Adverse Events	12 months	Randomization	x (p%), p-value
Subjects with serious adverse events of interest within 30 days	Safety analysis set	Serious adverse events of interest	30 days	Randomization	x (p%), p-value
Subjects with death and stent thrombosis within 12 months	Safety analysis set	Death and Stent Thrombosis	12 months	Randomization	x (p%), p-value
DAPT and Anti-Thrombotic Medication	ITT	DAPT and Anti-Thrombotic Medications used	Baseline	Randomization	x (p%), p-value

COPY

Listing of Listings

Title	Population	Display Variables	Time Point	Sort Variable
Subjects not cooled	ITT	Randomization, Subject ID, Reason for not cooling	Baseline	Randomization
Protocol Deviations	ITT	Reasons for deviation	Baseline, 4-6 day, 30 days, 12 months	Randomization, Subject ID
Device Deficiency	ITT	Device type, device disposition, deficiency description	Baseline	Randomization, Subject ID
Serious Adverse Events	ITT	Adverse Event Number, Adverse Event, Adverse event start date, Outcome, Procedure relatedness, Device relatedness	Baseline, 4-6 day, 30 days, 12 months	Randomization, Subject ID, AE number

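### The exploratory covariate model for infarct size is chosen by univariate screening and stepwise testing without correction, so its p-values are anti-conservative and weak effects that survive are overstated

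*SAP*

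**What the plan says.** The second paragraph of SAP Section 6.3 opens by saying that "separate univariate models may be considered for exploratory analysis: ischemic time, country and/or center". It continues "Analysis of covariance models will be used", and promises a coefficient, standard error, 95% interval and p-value. For failed model assumptions it gives one remedy: "Square root transformation will be used if assumption is violated".

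Model building follows in three steps, all on the same outcome:

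1. Only variables significant on their own go forward: "From among the variables with individually significant associations, after selection of single covariates from among any collections of highly collinear covariates".
2. The choice within a collinear set rests on each variable's univariate association with infarct size.
3. Then "a multivariate model will be built using forward and backward stepwise variable selection, to determine the variables with independently significant associations with risk", with 0.05 as the criterion.

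No shrinkage, validation or correction for selection is stated. Section 6.7 sets all analyses other than the primary efficacy and the safety tests at two-sided 0.05, with no multiplicity adjustment mentioned for them.

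The Section 13 table "Association of infarct size with covariates" lists eight variables: age, BMI, sex, pre- and post-procedure TIMI flow, door-to-balloon time, ischemic time and temperature at PCI. It is planned for both ITT and PP, and a p-value is its only statistic. Country and centre, named in Section 6.3, are not in it.

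For subgroups, Section 6.3 says that a "p-value will be reported for each group as appropriate depending on final linear regression model". It does not define that final model.

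**The concern.** A variable reaches the selected model only by passing significance tests on the data that then supply its p-value. An unrelated variable that gets in is significant by construction, and its nominal 95% interval excludes the true value of zero. A weak true predictor gets in mainly when chance has enlarged its estimate. Ordinary p-values and intervals ignore both effects, so calling the survivors independently significant claims more than the method can show.

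Three features of the text make this worse:

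- **The candidate pool is not fixed.** Section 6.3 and Section 13 give different lists, and centre may have up to 70 levels (Section 6.6).
- **The treatment term is left open.** The text does not say whether randomised treatment is kept.
- **Some candidates arise after randomisation.** Temperature at PCI is changed directly by cooling and could stand in for treatment. Post-procedure TIMI flow also follows randomisation.

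At stake is how the covariate findings are read and reused, not the trial's primary conclusion.

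**Working it through.** **Inputs from the SAP.** The SD is 12 %LV, with 384 evaluable subjects (Section 5). The screening and stepwise criteria are 0.05 (Section 6.3). There are three candidates in Section 6.3 or eight in Section 13. Enrolment was never completed (Section 6.4), and the actual number is not given.

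**The plan's own figure.** The SAP gives none on this point, so only the sample size can be reproduced. Per arm, n = 2 × (z₀.₉₇₈ + z₀.₈₀)² × 12² / 3.5² = 2 × (2.014 + 0.842)² × 144 / 12.25 ≈ 192, or 384 in total. This agrees with Section 5.

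**Chance of a false finding if nothing is related.** For k independent candidates it is 1 − 0.95^k.

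- k = 3: 1 − 0.95³ = 0.14
- k = 8: 1 − 0.95⁸ = 0.34

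Simulating the full procedure with eight null candidates gave 0.32–0.33.

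**Simulation with true predictors.** Each run applied the univariate screen at 0.05, forward and backward stepwise selection at 0.05, and then ordinary least-squares intervals, with 1,500 runs per case. These inputs are assumptions: standardised continuous candidates, pairwise correlation 0.2, total SD 12, the true effects shown, and N = 100 as a lower case. Treatment was not a term in these runs.

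| N | Candidates | True effects (%LV per SD) | False share of selected | Overstatement of true effects | Coverage, all selected |
|---|---|---|---|---|---|
| 384 | 8 | 1.2 | 38% | 1.42 | 59% |
| 384 | 8 | 2.4 | 16% | 1.00 | 82% |
| 384 | 8 | 3.6 | 14% | 0.99 | 82% |
| 384 | 8 | 2.4, 2.4, 1.2 | 6% | 1.09 | 90% |
| 384 | 3 | 2.4 | 6% | 1.00 | 93% |
| 100 | 8 | 1.2 | 68% | 2.46 | 27% |
| 100 | 8 | 2.4 | 37% | 1.37 | 60% |
| 100 | 8 | 3.6 | 20% | 1.08 | 78% |
| 100 | 8 | 2.4, 2.4, 1.2 | 13% | 1.60 | 78% |
| 100 | 3 | 2.4 | 16% | 1.34 | 81% |

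Divided by the SD of 12, effects of 1.2, 2.4 and 3.6 are 0.1, 0.2 and 0.3 SD of infarct size. Most of the lost coverage comes from false selections. Among true predictors alone, coverage was 94% or more in every case at N = 384, and 85–97% at N = 100.

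**The case against.** The other side has a good deal that stands.

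- **Status.** The models are optional and labelled exploratory. The primary test in Section 8.1 is an unadjusted t-test or Wilcoxon test, so no success criterion depends on them.
- **Treatment.** A reader might infer that treatment is left to the selection. The SAP does not say so: it names analysis of covariance and is silent on the treatment term. As an illustration only, treatment (true effect −3.5 %LV) was put in the selectable pool with temperature at PCI, at assumed arm means of 33.5 and 36.3 °C. It was kept in 61% of runs at N = 384 and 21% at N = 100, partly through limited power alone.
- **Extent.** A reader might infer that the selected predictors are mostly artefacts. The figures support that only when nothing is truly related, or when effects are weak and the sample is small.
- **The 34%.** This is ordinary multiplicity over eight null tests, and a fixed model tested term by term would give about the same. Section 13 also does not say that its eight variables are the stepwise pool.
- **Intervals.** The promise of 95% intervals comes before the stepwise step, so intervals for the selected model are not clearly planned. One Section 13 figure does give a coefficient and interval for ischemic time.
- **Subgroups.** A reader might infer that subgroup tests use the stepwise model. Section 6.3 describes a separate interaction model, and the phrase about the final model may only govern which test is reported. The text is ambiguous.
- **Transformation.** Section 8 also allows transformation as needed after residual plots, so the square-root rule is not the only one in the SAP.

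None of this answers the central point. The exploratory label does not justify a claim of independent significance after uncorrected selection, and the Section 13 table will be reported.

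**Conclusion.** The point holds as a defect of an exploratory analysis. Followed as written, Section 6.3 gives anti-conservative p-values in the selected model, and would give anti-conservative intervals if they were reported.

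At the planned 384 subjects with eight candidates, the false share runs from about 38%, with 1.4-fold overstatement, for one weak predictor, down to 14–16% for one moderate predictor. It is about 6% with three true predictors, or with three candidates of which one is moderate. At an assumed 100 subjects the range is 13–68%. These figures rest on assumed effect sizes, correlation 0.2 and continuous candidates. Centre as a many-level factor was not simulated.

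The primary efficacy result is untouched. The change is worth making because the wording claims more than the method can deliver and the remedy is cheap.

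**What to change.** In Section 6.3:

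- Replace the screening and stepwise sentence with one prespecified linear model in %LV. It contains treatment, always retained, and a short fixed list of pre-randomisation covariates, all kept whatever their p-value. Age, sex, BMI and onset-to-randomisation time would serve. The last should be derivable from Section 7.3 as total ischemic time minus randomisation-to-balloon time, assuming that ischemic time runs from onset to balloon.
- Report every coefficient, standard error and 95% interval as descriptive, and drop the claim of independent significance.
- Keep temperature at PCI and post-procedure TIMI flow out of this model, or present them separately and label them post-randomisation.
- Use heteroscedasticity-robust standard errors for unequal variance only. Like the square root, they do not cure dependence or non-linearity.
- State that subgroup interactions do not depend on a data-selected model.

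In Section 13, align the covariate list with Section 6.3 and add the coefficient, standard error and interval to the table.

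The cost is SAP wording and one table shell, and programming becomes simpler. The plan gives up a data-driven shortlist of predictors. A fixed model does not remove multiplicity across its terms, but it shows all of them without filtering on significance.
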